 4. IL-6
 5. NT-BNP
 6. Urine pregnancy test for women of child-bearing potential
- CPET-Innocor™
- Assess medication compliance
- Collect all study drug and study drug containers. Study drug will be collected from subjects at BWH.

Drugs and Dosing

The proposed dose of ambrisentan was selected based on retrospective data demonstrating that spironolactone is most effective in combination with ambrisentan at 5 mg/d and 10 mg/d.⁴ The rationale for the proposed spironolactone dose and treatment timing is based on pharmacological studies⁵ and data from clinical trials indicating that 50 mg/d inhibits vascular mineralocorticoid receptor-dependent activity sufficiently in patients with forms of cardiovascular disease relevant to PAH.⁶ We selected a wash out period of 21 days, which is of sufficient duration to extinguish relevant circulating drug levels of this therapy as well as effects of spironolactone on pulmonary vascular function and structure,^{1,2} and is comparable to previously published reports studying the effects of spironolactone on insulin resistance in heart failure⁷ and endothelial function in obesity.⁸

Ambrisentan (a selective endothelin type-A [ETA] receptor antagonist) is an FDA approved treatment for PAH. Participants who qualify to be enrolled in the study are receiving ambrisentan as standard of care for treatment of PAH. Participants must be on a stable dose of ambrisentan (5mg/d – 10 mg/d for >3 mo.). Ambrisentan is taken once daily, preferably in the morning, with or without food.

Spironolactone is a synthetic, steroidal antimineralcorticoid agent with additional antiandrogen and weak progestogen properties, as well as some indirect estrogen and glucocorticoid effects, which is used primarily as a diuretic and antihypertensive, but also for the purpose of reducing elevated or unwanted androgen activity in the body. It acts predominantly as a competitive antagonist of the aldosterone receptor, and belongs to a class of pharmaceutical drugs known as potassium-sparing diuretics. Spironolactone is an FDA approved medication.

The spironolactone tablets provided as 25, 50 or 100 mg strengths.

Placebo tablets are identical in size, shape, and color to spironolactone.

Eligible participants will then be randomized to receive placebo or spironolactone (50 mg/d) for 90 days (Phase I). At the completion of Phase I, participants will undergo repeat end-point assessment followed by a 21-day drug wash out period. Then, the 90 day crossover phase of the trial will occur (Phase II), in which participants randomized to placebo in Phase I will be treated with spironolactone (50 mg/d) in Phase II and *vice versa*. At the conclusion of Phase II, end-point measures are reassessed.

Once all entry criteria have been met and random treatment assignment confirmed, the first dose of study drug 50 mg should be taken by the subject with or without food. Study drug should be taken once daily, preferably in the morning.

Spironolactone/placebo will be dispensed to patients at Brigham and Women's Hospital (BWH) at the time they are having the CPET-Innocor™ at Baseline, Phase 1 and Day 1, Phase II Visits. All drug containers will be returned to BWH at Day 90, Phase I and Day 90, Phase II Visits.

Study drug to be stored at room temperature.

Side effects of spironolactone include headache, diarrhea, cramps, drowsiness, rash, nausea, vomiting, irregular menstrual periods, and irregular hair growth. Fluid and electrolyte imbalance such as hyperkalemia may occur. Gynecomastia may also occur and is related to dose and duration of therapy. It usually reverses upon discontinuation of spironolactone.

VI. Biostatistical Analysis

Endpoints

Study Primary End-points: A two-primary end-point study model¹⁰ will be used in this study, to include change from baseline (study drug day 1) at study drug day 90 for each of the two trial phases in (i) 6 minute walk distance and (ii) peak VO₂ at the completion of exercise as a determinate of overall cardiopulmonary fitness.

Study Secondary End-points: The secondary end-points are change from baseline (study drug day 1) at study drug day 90 for each of the two trial phases for cardiac output assessed noninvasively by the Innocor™ device¹¹, the minute ventilation/volume of expired carbon dioxide (V_E/VCO₂) slope at the completion of exercise as assessed by the Innocor™ step protocol; echocardiographically assessed RV geometry (RV dimensions, RV fractional area change, RV area and volume), pulmonary artery acceleration time, morphology of the pulmonary artery outflow tract Doppler envelope, and tricuspid annular plane systolic excursion (TAPSE) to assess RV function; and quality of life assessed by the SF-36 scale.

Innocor™ assessments and analysis of echocardiography and Innocor™ results will be performed at a single core facility (Brigham and Women's Hospital).

Additional Measures: Assessing volume status

Compared to other traditional diuretic pharmacotherapies, spironolactone induces a weak natriuretic effect to modulate subtle changes to circulating blood volume.⁴ However, in order to assess the potential effect of spironolactone on outcome in PAH due to diuresis rather than change in pulmonary vascular function, several clinical measures indicative of volume status will be assessed. These include, regular body weight measurement and jugular venous pressure monitoring assessed at 4-week intervals according to previously published methods,¹² as well as a record of all study participants' relevant cardiovascular medication (and doses) such as loop and thiazide diuretics. Tracking this information will allow for the study investigators to analyze outcome results according to diuretic status, and provide information regarding timing and extent to which spironolactone influences circulating plasma volume clinically.

Statistical Methods

A two-primary end-point study model will be used in the proposed trial, which is akin to previously published clinical trial reports in pulmonary arterial hypertension,¹⁰ as follows:

Physiological Measure of Performance: Peak VO₂

Peak oxygen consumption (pVO₂) is a continuous response variable, and we will be comparing ΔpVO_2 from baseline to 90 days, and baseline to 180 days between control and intervention group. Difference in ΔpVO_2 , from baseline (day 1) to day 90, the treatment effect, will be compared using a 2-sided, paired Student's t test. There are few data on the distribution of change in VO₂ with interventions. Our prior studies, in patients with congenital heart defects, have shown that change in pVO₂ is normally distributed.¹¹ In our observational study of patients with congenital heart disease, those who engaged in frequent activity increased pVO₂ by 1.8 ± 3.2 mL/kg/min. This study included very heterogeneous diagnoses and levels of baseline pVO₂, and we anticipate the variance of the current study to be significantly lower. A true 1.0 mL/kg/min ΔpVO_2 difference would be clinically important. If the true difference in mean response of matched pairs is 1.0 ± 1.7 mL/kg/min, we will need 25 subjects to be able to reject the null hypothesis with probability (power) 0.80

with associated Type I error of 0.05. To account for loss to follow-up or incomplete data, we will enroll 30 subjects. Calculations performed using PS power and sample size program.¹²

Statistical analyses

The proposed strategy for statistical analyses of end-points is illustrated in Figure 2. All end-points will be analyzed by comparing change in outcome from study drug day 1 to study drug day 90. End-points will be summarized descriptively by treatment, and treatment effect will be compared using methods appropriate for a 2x2 crossover design. We do not anticipate substantial carry over effects by placebo or spironolactone on outcome measures due, in part, to the lengthy study drug wash out period.

[figure not shown]

Figure 3. Stastical ananlysis schema. The CAPS-PAH trial proposes a prospective, randomized, placebo-controlled cross-over design to test the effect of spironolactone therapy on outcome in pulmonary arterial hypertension. In Phase I, patients on stable therapy with ambrisentan (5 -10 mg/d) will be randomized to treatment with placebo or spironolactone (50 mg/d) and testing relevant to the study end-points, such as peak volume of oxygen consumption (pVO_2), will occur at study day 1 and day 90. Following a 21-day drug wash out period, subjects will enter into Phase II of the trial, which is characterized by cross-over to opposite therapy of Phase I. Repeat end-point assessment will be performed at study drug day 1 and study drug day 90 of Phase II. Change in performance on end-points from study drug day 1 at study drug day 90 while receiving spironolactone will be compared to change in

performance from study drug day 1 at study drug day 90 while receiving placebo, using a 2-sided, paired Student's t test. Carryover and period effects will be tested using appropriate methods prior to testing the treatment effect.

VII. Risks and Discomforts

Risks of Spironolactone:

Common Side Effects

- Skin rash
- Headache
- Dizziness
- GI symptoms of nausea, vomiting, gas, diarrhea and stomach pain
- Cramps
- Drowsiness
- Irregular menstrual periods
- Irregular hair growth

Less Common Side Effects

- Hyperkalemia
- Gynecomastia

Risks of the 6- Minute Walk Test:

- Fatigue
- Fainting
- Muscle soreness
- Muscle strain or injury.

Risks of Blood Draws:

- Bruise or pain where the blood samples are taken
- Small risk of infection

- Lightheadedness and/or fainting

Risks of Cardiopulmonary Exercise Test with Innocor™

- Increased dyspnea
- Fatigue
- Muscle soreness
- Chest pain
- Irregular heart beat
- Heart attack which has happened rarely

Participants will be monitored constantly during this test.

VIII. Potential Benefits

Participants may not benefit from taking part in this study.

Potential benefit may be to answer the hypothesis of the current proposal is that the addition of spironolactone (50 mg/d) to selective ET_A inhibition (standard therapy) with ambrisentan (5-10 mg/d) is more effective than standard therapy alone at improving cardiopulmonary fitness and quality of life in patients with PAH.

IX. Monitoring and Quality Assurance

Data Safety Monitoring Plan

The principal investigator will designate a Medical Monitor (TBD) to be responsible for the safety monitoring of the data for this protocol. A Medical Monitor will be appropriate to monitor data and safety because:

- endpoints are not serious irreversible events;

- the intervention is not high risk and the effects of which would not generally be so compelling as to ethically warrant early termination for effectiveness;
- this protocol is offering short term treatment where effects are evaluated over periods of a few months;
- a smaller number of subjects where the study is completed quickly and the risk can be adequately assessed through simple comparisons.

The study is a three center study (all local hospitals) with a total of thirty subjects being enrolled. Subjects to be enrolled will have the diagnosis of PAH and being treated with combination therapy: ambrisentan 5-10 mg every day and sildenafil or tadalafil at any pulmonary hypertension therapeutic dose.

The safety data will be reviewed as the research team obtains information from the subjects. This information will be obtained at every clinic visit or by telephone.

Conference calls for all 3 sites will be made every 10-12 weeks. During conference calls a discussion of safety issues will be discussed.

The range of possible study events that could have an important impact on the risks and benefits of research subjects is narrow. All events of toxicity that occur will be promptly submitted to the IRB.

Confidentiality

In order to maintain subject privacy, all case report forms (CRFs), study drug accountability records, study reports, and communications will identify the subject by initials and the assigned subject number. The Investigator will grant auditor(s) from regulatory authority(ies) access to the subject's original medical records for verification of data gathered on the CRFs and to audit the data collection process. The subject's confidentiality will be maintained and will not be made publicly available to the extent permitted by the applicable laws and regulations.

References

1. Badesch DB, et al. Diagnosis and assessment of pulmonary arterial hypertension. *J Am Coll Cardiol* 2009 Jun 30
2. Galie N, et al. Guidelines for the diagnosis and treatment of pulmonary hypertension. *Eur Respir J*. 2009 Dec
3. Simonneau G, et al. Updated clinical classification of pulmonary hypertension *J Am Coll Cardiol* 2009 Jun 30

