7. Baseline 6-Minute Walk Distance \geq 50m.

Exclusion Criteria

1. Substantial Primary Lung disease
 - FEV₁/FVC <0.6 and FEV₁ <70% predicted
 - DLCO <30% predicted
 - Pulmonary fibrosis¹⁴
2. Left ventricular ejection fraction < 50%
3. Pulmonary capillary wedge pressure > 16 mmHg
4. Aortic valve disease
5. Ischemic heart disease

6. Systemic hypotension (SBP <90 mmHg)
7. Co-existing treatment with other endothelin receptor antagonists or prostacyclin analogues
8. New York Heart Association Functional Class IV
9. Chronic thromboembolic pulmonary hypertension
10. Known or suspected pulmonary veno-occlusive disease
11. Serum creatinine >2.0 mg/dL in women, Serum creatinine >2.5 mg/dL in men
12. Baseline serum potassium \geq 5.0 mEq/L
13. Participation in ongoing drug/intervention-based clinical trial
14. Pregnancy
15. Unable to provide consent

IV. Subject Enrollment

To test our hypothesis, we propose a prospective, double blind, placebo-controlled clinical study involving 30 patients with World Health Organization (WHO) Group 1 pulmonary hypertension randomized to receive placebo or spironolactone (50 mg/d) for 90 days using a cross-over trial design (Figure 1).

[figure not shown]

Figure 1. Proposed patient flow strategy for enrollment and follow up in the CAPS-PAH study. SPIRO, spironolactone (50 mg/d); 6MWT, 6-minute walk test; d, days.

Participants on a stable dose of ambrisentan (5mg/d – 10 mg/d for >3 mo.) enrolled in this study will undergo baseline biochemical, functional, physiological, and clinical testing, which comprises the study end-points. Eligible participants will then be randomized to receive placebo or spironolactone (50 mg/d) for 90 days (Phase I). At the completion of Phase I, participants will undergo repeat end-point assessment followed by a 21-day drug wash out period. Then, the 90 day crossover phase of the trial will occur (Phase II), in which participants randomized to placebo in Phase I will be treated with spironolactone (50 mg/d) in Phase II and *vice versa*. At the conclusion of Phase II, end-point measures are reassessed.

V. Study Procedures

Clinical Assessments

1. Medical History and Physical Examinations

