Subjects enrolled at Boston Medical Center and Tufts Medical Center will have research biomarker blood samples collected at Brigham and Women's Hospital at Baseline and Day 90 of Phase I, and Days 1 and 90 of Phase II. The research laboratory samples will be collected at BWH when they are here for the Cardiopulmonary Exercise Test (CPET) with Innocor. The samples will be collected at BWH because the research laboratory testing will be performed in [name]'s laboratory. The CPET-Innocor® will be performed prior to Baseline Visit for all subjects enrolled at BWH. Subjects enrolled at BMC and Tufts will have CPET performed after the consent form is signed, but is a clinically indicated procedure.

Approximately 30 mL of blood will be collected

7. Echocardiography

Echocardiography (ECHO) will be assessed at Baseline and Day 90 of Phase I, and Days 1 and 90 of Phase II. The ECHO will evaluate the right ventricle. It is anticipated that by decreasing pulmonary vascular fibrosis to improve pulmonary vascular function, improvements to RV loading will associate with favorable changes to cardiac output, and, consequently, PAH symptomatology.

8. Cardiopulmonary Exercise Test with Innocor™

A previously standardized cardiopulmonary exercise test graded-exercise (CPET) protocol will be used to assess change in non-invasively measured cardiac output and peak oxygen consumption (pVO₂) from baseline (study drug day 1) at study drug day 90 for each of the two trial phases. Refer to Appendix F for description of CPET. All CPET-Innocor required for the protocol will be performed at BWH.

Functional capacity will be assessed per CPET protocol and change in distance on the 6MWT from baseline (study drug day 1) at study drug day 90 for each of the two trial phases.

9. Adverse Events (AE)

AEs will be captured from the time the informed consent form is signed. All AEs should be followed until either resolution (or return to normal or Baseline values), until they are judged by the Investigator to no longer be clinically significant, or for up to 30 days if the AE extends beyond the final visit. All severe AEs (SAEs) should be followed until resolution, death, or the subject is lost to follow-up even if they are ongoing more than 30 days after completion of the final visit. Appendix E provides the guidelines and definitions for recording AEs.

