Table 1. Proposed evaluation/diagnostic testing time points post-randomization in the CAPS-PAH study. Liver function markers are aminotransferase/alanine aminotransferase; Renal function markers are creatinine and serum potassium; 6-MWT, 6-minute walk test; NT-BNP, N-terminal pro-type brain natriuretic peptide; Wash, wash out for 21 days.

Baseline Visit (Day 1, Phase I):

Baseline visit will require a visit to the enrolling center and then a visit to BWH for CPET-Innocor and collection of research biomarker blood samples. The visit to BWH needs to be scheduled 24 to 72 hours after the visit at the enrolling center.

Written informed consent must be obtained from the subject. Participation in this study is voluntary. The nature of the study will be fully explained to each subject during the informed consent process and the subject will have the opportunity to ask questions. An informed consent form will be signed by the subject and the person performing the consent discussion, and retained by the Investigator. A copy of the signed informed consent form will be given to the subject.

Assessments to be performed during visit at local sites:

- Inclusion/Exclusion criteria.
- Medical history to include PAH history and PAH treatment history.
- Physical examination (i.e., jugular venous pressure) and vital signs (blood pressure, heart rate, and respiratory rate). Weight and height to be measured.
- SF-36 questionnaire
- 6-Minute Walk Test/Borg Score.
- Laboratory tests:
 1. Liver function markers (AST/ALT)
 2. Renal function markers (creatinine and potassium)
 3. Inflammatory Biomarkers
- Echocardiography
- Dispense weight diary

Assessments to be performed at BWH:

- Laboratory tests to be performed at BWH at time of CPET-Innocor.
 1. Troponin-I
 2. Collagen III
 3. N-terminal procollagen type I

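### In the visible text, nothing requires potassium, creatinine and SBP to be checked against the entry limits before placebo-first patients take their first spironolactone at Phase II Day 1

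*Combined protocol and SAP*

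**What the plan says.** **Limits.** Section III, Exclusion Criteria, lists "Systemic hypotension (SBP <90 mmHg") as item 6, "Serum creatinine >2.0 mg/dL in women, Serum creatinine >2.5 mg/dL in men" as item 11, and "Baseline serum potassium" of 5.0 mEq/L or more as item 12.

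**When they are applied.** In section V, the item "Inclusion/Exclusion criteria" appears in the list for the Baseline Visit (Day 1, Phase I) and in no other visit list. Drugs and Dosing adds: "Once all entry criteria have been met and random treatment assignment confirmed, the first dose of study drug 50 mg should be taken". Randomization happens once, at the Phase I baseline.

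**Who starts spironolactone when.** Drugs and Dosing states that "participants randomized to placebo in Phase I will be treated with spironolactone (50 mg/d) in Phase II". Table 1 places the start of Phase II at day 112.

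**What happens at Phase II Day 1.** The enrolling center takes vital signs, including blood pressure, and draws creatinine and potassium. The patient then visits BWH 24 to 72 hours later for the exercise test, and study drug is dispensed there. Neither the visit list nor Drugs and Dosing attaches a laboratory or blood pressure condition to that step.

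**Other monitoring.** The visit lists schedule potassium, creatinine and blood pressure at Phase I Days 14, 56 and 90 and at Phase II Days 14, 56 and 90. Section IX has safety data reviewed as they come in and provides for a Medical Monitor. Appendix E recognises interruption and withdrawal of drug as actions.

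**Known risk.** Drugs and Dosing says of spironolactone: "Fluid and electrolyte imbalance such as hyperkalemia may occur".

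**The concern.** The three limits are the protocol's only written numerical limits on potassium, creatinine and systolic pressure. In the spironolactone-first sequence they stand directly before the first active dose. In the placebo-first sequence the same check stands before a placebo dose, and the first active dose follows at Phase II Day 1 with no such check required. A placebo-first patient whose potassium has reached 5.0 mEq/L by then can be given spironolactone without any departure from the written plan, although the same value would have kept that patient out in Phase I.

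What is at stake is patient safety at one dispensing step, for a drug whose named risks include hyperkalemia. The values needed to close the gap are already scheduled.

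**Working it through.** **1. The two first active doses side by side.**

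| | Spironolactone-first | Placebo-first |
|---|---|---|
| First spironolactone dose | Phase I Day 1 | Phase II Day 1 |
| Eligibility check listed at that visit | Yes | No |
| Dosing text tied to entry criteria | Yes | No (tied to the one randomization) |
| Potassium, creatinine, BP scheduled at that visit | Yes | Yes |
| Written condition before the first active dose | Yes, through the entry criteria | None found |

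**2. Age of the check and age of the data.** These differ.
- Formal check against the limits: 90 + 21 = 111 days before the placebo-first patient's first spironolactone dose (equally 112 - 1 = 111).
- Last routine values before Phase II Day 1: Phase I Day 90, about 21 days earlier.
- Most recent values: the Phase II Day 1 draw itself, 24 to 72 hours before dispensing.

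**3. Patients concerned.** Enrolment is 30. The ratio is not stated; 1:1 is assumed.
- Nobody lost: 30 / 2 = 15.
- All 5 allowed losses (30 - 25) occur before Phase II, spread evenly: 25 / 2 = 12.5, so 12 or 13.

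This is the size of the sequence reaching Phase II, not the number past a limit.

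**4. Chance that it matters.** The documents give no rate for crossing a limit, so the rate r is an assumption. Expected number = m × r; chance of at least one = 1 - (1 - r)^m.

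| Assumed r | Expected, m = 12 | Expected, m = 15 | At least one, m = 12 | At least one, m = 15 |
|---|---|---|---|---|
| 2% | 0.24 | 0.30 | 22% | 26% |
| 5% | 0.60 | 0.75 | 46% | 54% |
| 10% | 1.2 | 1.5 | 72% | 79% |

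At two of the three rates fewer than one patient is expected.

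**5. What holds could cost in power.** First the plan's own figure: paired t test, difference 1.0, SD 1.7, two-sided alpha 0.05, noncentrality (1.0/1.7) × √n. Power is 0.788 at n = 24 and 0.806 at n = 25, so the stated 25 reproduces.

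If the check applies to all 30, the expected number held is 30r = 0.6, 1.5 or 3. Take 3 and suppose every one is lost as a pair:
- No other losses: 30 to 27 pairs, power 0.876 to 0.837.
- Loss allowance already used: 25 to 22 pairs, power 0.806 to 0.749.

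**6. Time available for a repeat.** Table 1 gives Phase II Day 1 a window of ±5 days. If it also covers the BWH visit (assumption), and BWH follows the enrolling-center visit by 1 to 3 days:
- Enrolling-center visit on the nominal day: 5 - 3 = 2 to 5 - 1 = 4 days left after the BWH visit.
- Enrolling-center visit 5 days early: 10 - 3 = 7 to 10 - 1 = 9 days left.

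**The case against.** The strongest reply is that these patients are watched throughout. From the 111-day interval a reader might infer that placebo-first patients reach spironolactone on stale safety data. The documents do not support that: the Phase I visits and the Phase II Day 1 draw supply recent values, and further checks follow at Phase II Days 14 and 56. This part of the reply stands, and it narrows the point to the missing decision rule.

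Second, a bare dispensing line proves little alone, because the Phase I baseline list has the same line. That is fair. The difference is that other text conditions the Phase I dose on the entry criteria, and no corresponding text was found for Phase II.

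Third, a reader might infer that results from the other two centers never reach BWH. No transfer step is written, but none is written for Phase I either, so the plan apparently relies on ordinary communication between sites, and a missing sentence does not show that results go unread. BWH also enrolls its own patients (the protocol says of the exercise test that it "will be performed prior to Baseline Visit for all subjects enrolled at BWH"). No transfer between sites is needed for them, yet the review step is absent for them too.

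Fourth, the exclusions are entry criteria, and the potassium item is worded as a baseline value. Using them at Phase II turns them into a post-randomization condition for starting drug. That is a real design choice and should be made openly.

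Finally, Figure 1 is not shown and Table 1 is broken in extraction. A rule that appears only in the figure cannot be excluded.

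**Conclusion.** The point holds in limited form. In the visible text, the SBP, creatinine and potassium limits are formally applied only before the first Phase I dose, and a placebo-first patient's first spironolactone dose does not depend on the values taken for that visit. General safety review and clinical judgment may well catch an abnormal value, but neither is required before dispensing and neither carries a limit.

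About 12 to 15 patients are in this position, given 1:1 allocation and between 0 and 5 evenly spread losses. How many would be past a limit is unknown; the 2%, 5% and 10% rates only illustrate a range.

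A reader might also infer that the gap biases the treatment comparison. Nothing in the documents supports that, and no effect on the primary analysis is claimed. This is a modest safety amendment that should be made.

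**What to change.** Add to the Day 1, Phase II list, for all patients because assignment is blinded:

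> Before study drug is dispensed, BWH confirms that the Phase II Day 1 potassium, creatinine and SBP do not meet exclusion criteria 6, 11 or 12. If any does, drug is held and the value repeated within the visit window. Phase II drug is not started if the value is still past the limit.

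Report holds and non-starts by sequence, since this acts after randomization. If Figure 1 already carries such a rule, repeat it in the visit list. The change uses the entry limits as the limit for starting Phase II drug; it adds no routine test. It does not supply a rule for values found later on treatment (Days 14 and 56).

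Costs:
- Laboratory turnaround is not documented. A late result would delay dispensing, and a hold may need another BWH visit and lengthens the wash-out.
- A hold that outlasts the window may mean repeating the Phase II baseline tests or losing the pair, because change is measured from study drug day 1. The power figures above bound this under the assumed 10% rate with every held pair lost.
- Some holds will fall on spironolactone-first patients about to start placebo, and any residual drug effect could make holds differ by sequence.
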